1.1. Background

Preterm birth (PTB), defined as birth less than 37⁺⁰ weeks gestation, is a significant health issue and is the most important single determinant of adverse infant outcome with regards to survival and quality of life(4). Morbidity is inversely correlated to gestational age, and the most significant adverse outcomes are associated with very preterm birth, defined as occurring less than 32⁺⁰ weeks gestation. Preventative measures which prolong fetal gestation by 1 week, such as those proposed by this study, could save health services £939 million per year in England and Wales(5).

The insertion of a suture around the cervix under regional anaesthesia is an established management strategy in those women at high risk of preterm birth. There is little consensus on the optimal procedure, technique or timing of insertion. Its mechanism of action has been hypothesised as not only supportive but as reinforcing the immunological barrier which protects the fetus from ascending vaginal infection. The benefit of an ultrasound indicated cerclage following evidence of cervical shortening ($\leq 25\text{mm}$) on transvaginal ultrasound scan has been reported to demonstrate a significant reduction in delivery <35 weeks gestation compared with expectant management (6).

The primary risk factor for PTB in multiparous women is a previous PTB(7). Emerging evidence has shown an association between late miscarriage (LM) (14-24 weeks) and PTB in women with a history of full dilatation caesarean section (FDCS) at term, affecting approximately 13.5% of these women. This is hypothesised to be due to a uterine incision, which is inadvertently too low, in or near to effaced cervical tissue. This occurs because the cervix becomes continuous with the lower segment of the uterus at full dilatation and the anatomy can often be distorted. Disruption and scarring of this cervical tissue is thought to result in cervical incompetence in future pregnancies. The association between FDCS and LM/PTB has only recently been recognised and it presents a pressing clinical problem.

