2.2. Study objectives

2.2.1. CRAFT-OBS: a study of risk and management in women with a history of CS in labour

- i. Determine the incidence of LM and PTB (prior to 37 weeks) in women with previous CS in labour stratified by cervical dilatation.

- ii. If ultrasound measured cervical length and quantitative fibronectin are carried out, this data will be collated and help evaluate the ability of these tests to determine risk of preterm birth in women with a history of in labour caesarean.

2.2.2. CRAFT-RCT: a trial of USS indicated cerclage in women with history of FDCS

- i. Determine if an ultrasound-indicated cervical cerclage is effective management in women with a history of FDCS and cervical shortening (<25 mm) in preventing LM or PTB <34 weeks gestation. Evaluate the impact of intervention on short-term fetal and neonatal outcomes, assessed as a composite of fetal and perinatal death and major morbidity.
- ii. Assess the impact of both management strategies (i.e. cerclage and observation) on health economic outcomes for mother and infant in terms of number of nights in hospital; cost data to hospital discharge/28 days post delivery.

2.2.3. CRAFT-IMG: a sub-study evaluating imaging methods for assessing risk and management of women with a history of FDCS

- i. Ascertain whether MRI or ultrasound (or a combination of the two) can accurately predict PTB when abnormalities are detected in the cervix.
- ii. Identify which women are most likely to benefit from intervention.

3. Study Design

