3.4. Expected study duration

Recruitment will be conducted over a 24 month period. The end of the study will be defined as 28 days post-delivery or discharge from hospital (whichever sooner) of the last recruited participant and infant. Women will be followed-up until postnatal discharge. The end of the study will be reported to the REC and Regulatory Authority within 90 days, or 15 days if the study is terminated prematurely.

4. Study Endpoints

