4.2. CRAFT-RCT

Primary endpoint:

- i. Delivery <34 weeks gestation (powered)

Secondary endpoints:

- i. Adverse perinatal outcome, defined as composite outcome of death (ante-partum/intra-partum stillbirths plus neonatal deaths prior to discharge from neonatal services) or one/more of intraventricular haemorrhage, periventricular leukomalacia, hypoxic ischaemic encephalopathy, necrotizing enterocolitis, bronchopulmonary dysplasia and sepsis.
- ii. Gestation at delivery.
- iii. Requirement for rescue cerclage (bulging fetal membranes).
- iv. Time between intervention and delivery.
- v. Health costs at 28 days post-delivery.

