Serial MRI scans will be performed on a 3-Tesla MRI scanner at St Thomas' Hospital. Conventional imaging will include high resolution T1 and T2 weighted images as well as diffusion datasets. The first advanced protocol transvaginal ultrasound and MRI will occur at any time from 20 weeks gestation. Where delivery has not occurred, further imaging will be offered (up to a maximum of 3 MRI and 3 of these transvaginal ultrasound scans).

Outcome data: All participants' data will be collated up until postnatal discharge. Neonates will be followed up until discharge or 28 days (whichever is sooner). Prompts on the database will alert the research midwife/assistant when each trial participant reaches her delivery date. Birth registers and in-patient records will be used to track hospital admissions and pregnancy outcomes. Outcome data (medical and economic) will be collected by review of NHS Maternity and medical records. If information is unavailable, e.g. if the delivery occurred elsewhere, the patient, patient's GP or other hospital will be contacted. Gestational age will be calculated using Study Protocol: **Cerclage After Full-dilatation caesarean-section**

IRAS ID:261294

REC: REC 19/LO/1270

Version 2.0

Date: 10.09.19

ultrasound estimated date of delivery predicted at the 12-15 week ultrasound scan. The primary and secondary outcome data will be collected from hospital records after discharge from neonatal care.

Source data and documents will be accessible by the research team only and any paper records will be stored in a locked cabinet in the Principal Investigators' offices. Electronic versions of these source documents are stored on Trust computers only and behind the NHS firewall. The study may be subject to inspection and audit by King's College London and Guy's and St Thomas' NHS Foundation Trust under their remit as sponsor and co-sponsor respectively, and other regulatory bodies to ensure adherence to GCP and the NHS Research Governance Framework for Health and Social Care.

The identifiable information obtained as part of this study will be managed in accordance with the General Data Protection Act (2018). The computerised information is protected by a software and hardware barrier, and the records are handled in the same way as hospital records. Data will be stored for 25 years in Trust firewalls/KCL Firewalls in accordance with legal requirements for the storage of maternity records.

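### The RCT cost endpoint leaves out everything after day 28, conflicts with text that runs to discharge, and distorts the cost comparison in a direction that depends on the mix of outcomes

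*Combined protocol and SAP*

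**What the plan says.** Protocol section 4.2 lists as the fifth secondary endpoint of CRAFT-RCT "Health costs at 28 days post-delivery". It gives no start for the costing period. Two other places apply the same limit. Section 7.3 states "Neonates will be followed up until discharge or 28 days (whichever is sooner". Section 3.4 ends the study at "28 days post-delivery or discharge from hospital (whichever sooner) of the last recruited participant and infant".

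Three places point to a different horizon:

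- The health economic objective in section 2.2.2 refers to nights in hospital and "cost data to hospital discharge/28 days post delivery". The slash does not say which limit applies.
- Section 7.3 also says "The primary and secondary outcome data will be collected from hospital records after discharge from neonatal care".
- The perinatal composite in section 4.2 counts "neonatal deaths prior to discharge from neonatal services", which can fall after day 28.

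Section 8 adds no costing method; it only refers back to the secondary endpoints of section 4.2.

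**The concern.** The trial aims to prevent late miscarriage and birth before 34 weeks (section 2.2.2), and the Lay Summary places the excess risk mainly below 28 weeks, together with many late miscarriages. Surviving babies born that early would be expected to stay in hospital well beyond 28 days. A 28-day cap then gives a birth at 26 weeks and a birth at 30 weeks the same number of counted days, so the endpoint cannot register a gain between them. Section 1.1 justifies the research partly by health-service savings from prolonging gestation by a week, which is the kind of effect the cap can hide.

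At stake is whether the trial's cost comparison can be interpreted. The conflicting horizons also leave the analyst to choose one after the data are in.

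**Working it through.** **The plan's own figure.** No figure is stated for costs. The only RCT figure that can be recomputed is the sample size in section 5: 10% against 5%, 80% power, 474 per group. With two-sided alpha 0.05 (not stated, assumed), the two-proportion formula gives 435 per group, and 474 with continuity correction, which matches. Then 474 / 0.95 = 499, stated as 500. The cost horizon does not enter this calculation.

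**Inputs for the cost check.** The 28-day limit comes from sections 3.4, 4.2 and 7.3. Postmenstrual age at discharge, D, is assumed to lie between 36 and 40 weeks for survivors.

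**Step 1: share of hospital days inside the window.** Stay = 7 × (D − birth week). Share = min(1, 28 / stay).

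| Birth week | Stay in days, D = 36 / 37 / 40 | Share counted |
|---|---|---|
| 24 | 84 / 91 / 112 | 33 / 31 / 25% |
| 26 | 70 / 77 / 98 | 40 / 36 / 29% |
| 28 | 56 / 63 / 84 | 50 / 44 / 33% |
| 30 | 42 / 49 / 70 | 67 / 57 / 40% |
| 31 | 35 / 42 / 63 | 80 / 67 / 44% |
| 33 | 21 / 28 / 49 | 100 / 100 / 57% |

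**Step 2: when is most of the stay lost?** More than half is lost when the stay exceeds 56 days, so when birth comes before D − 8 weeks: before 28 weeks if D = 36, 29 if D = 37, 30 if D = 38, 32 if D = 40. Below 28 weeks this holds across the whole assumed range. For all births under 32 weeks (very preterm in section 1.1) it needs D = 40.

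**Step 3: days are not costs.** If each of the first 28 days costs k times a later day, the share of cost counted is 28k / (28k + stay − 28). With k = 2 and D = 37 (both assumed):

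- 24 weeks: 56 / (56 + 63) = 47%
- 26 weeks: 56 / (56 + 49) = 53%
- 28 weeks: 56 / (56 + 35) = 62%

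The corresponding shares of days are 31%, 36% and 44%.

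**Step 4: effect on differences in days.** D = 37, two days for a term baby (assumed):

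| Change in outcome | True difference | Counted |
|---|---|---|
| Birth at 28 → 38 weeks | 63 − 2 = 61 saved | 28 − 2 = 26 saved |
| Birth at 26 → 30 weeks | 77 − 49 = 28 saved | 28 − 28 = 0 saved |
| Birth at 33 → 38 weeks | 28 − 2 = 26 saved | 28 − 2 = 26 saved |
| Loss at 22 weeks → survivor born at 26 weeks | 77 added | 28 added |

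**Step 5: an illustrative mix.** Suppose 15 births spread evenly over 24-33 weeks are averted (mean stay 59.5 days at D = 37) and 10 late miscarriages become survivors born at 26 weeks. True net saving = 15 × 59.5 − 10 × 77 = 892.5 − 770 = 122.5 days. Counted = 15 × 28 − 10 × 28 = 420 − 280 = 140 days. The short stays of the 15 later-born babies are left out; they would reduce both totals equally. Here the cap slightly overstates the saving.

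**The case against.** The best defence is that a 28-day horizon is stated openly, applies to both arms, and belongs to the last of five secondary endpoints. Every length of stay used above is an assumption. If early days are the expensive ones, the cost lost is smaller than the days lost. Nights in hospital are a separate item in section 2.2.2 with no limit attached there, and section 7.3 collects outcomes after neonatal discharge, so the full stay might be captured anyway.

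Much of this stands. The point is limited in weight, and step 3 confirms that the loss in cost can be well below the loss in days. Two parts do not stand. A common horizon does not give an undistorted difference when the arms may differ in what happens after it. And the section 7.3 sentence says when records are read, not which days are costed; the same section caps neonatal follow-up at 28 days.

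A reader might go further and infer that the cap always works against cerclage, with procedure costs counted in full and savings cut off. The documents do not support that. Section 4.2 gives no start for the costing, so full counting of the procedure is not stated. Late miscarriage is part of what the trial aims to prevent, and a loss replaced by a long-stay survivor adds cost that the cap also hides. Stays of 28 days or less lose nothing.

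**Conclusion.** The point holds as a cheap improvement. As written, the plan omits all costs after day 28, and its own passages disagree on the horizon. For survivors born before 28 weeks, the cap drops more than half of hospital days at any discharge age from 36 to 40 weeks. At 28-31 weeks the result depends on the discharge age: with births spread evenly over those weeks, the share counted runs from 62% (D = 36) to 38% (D = 40). The cost comparison is distorted, but its net direction depends on the unknown mix of averted early births, delayed births, late miscarriages and deaths.

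A reader might also take the planned effect (50 against 25 events per 500) and conclude that over half of the saving is lost: 25 × 59.5 = 1,488 nights against 25 × 28 = 700, a 53% shortfall. That figure should not be relied on. It counts nights rather than costs, gives every averted birth a full survivor's stay, and allows for no late miscarriages or deaths.

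The primary analysis and the 474 per group (500 recruited) are unaffected.

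**What to change.** - Define the cost endpoint in sections 4.2 and 2.2.2 as maternal and neonatal hospital costs and nights from randomisation to final hospital discharge of mother and baby, with costs to 28 days as a sensitivity cut.
- Align the neonatal follow-up rule in section 7.3 and the end-of-study definition in section 3.4. Changing the endpoint alone would contradict both.
- State that all randomised women are included, that late miscarriages, stillbirths and deaths enter at their actual costs, and that costs are reported alongside survival, so that a cheap early loss is not read as a benefit.

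The cost is the amended wording, extraction of later cot-days from records that section 7.3 already has staff review after neonatal discharge, and a somewhat later data lock for babies with long stays. No extra participants are needed.

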4.3. CRAFT-IMG

Primary endpoint:

- i. Alterations in imaging parameters between women with a full dilatation C-section in a previous pregnancy and either a cervix $\leq 25\text{mm}$ or a cervix $>25\text{mm}$ in this pregnancy which culminates in a preterm (<37 week) delivery.

5. Sample size and power calculation

All power calculations were performed by the trial statistician [name].

CRAFT-OBS: With estimated prevalence of 15% preterm birth rate prior to 37 weeks, and 16.2% of all deliveries being by emergency caesarean section; we will require data on 2200 women to estimate the event rate to 10% relative accuracy (e.g. 13.5% to 15.6%).

An average district general hospital has 4,000 deliveries per year, of which 648 (16.2%) might be by Emergency Caesarean. We aim to recruit 324 of these (50%) at a minimum of 7 study sites. At St Thomas' Hospital rather fewer deliveries (11%) are caesareans in labour; so we will aim for at least 20 sites, taking the assumptions above into account.

If we acquire data of cervical length and/or quantitative fetal fibronectin in this cohort, we will be able to validate these prediction tools. If we treat a short cervix of $\leq 25\text{mm}$, and a raised qfFN of $\geq 50\text{ng/ml}$ as positive tests, we anticipate a 75% sensitivity and 83% specificity from the literature for both tests (16).

Assuming 10% event rate, 1000 women (100 cases and 900 controls) would allow use to estimate the sensitivities of qfFN and CL to within 10% and the specificities to within 3% of the true value. The PPV would be estimated within 7% and NPV within 1.5% of their true values.

CRAFT-RCT: Pilot data indicates that at least 10% of all births and 70% of preterm births associated with FDCS occur before 34 weeks. In order to detect a reduction in this rate from 10% to 5% 474 women are required in each group to give 80% power. We will aim to recruit 500 in each arm in order to allow for 5% loss to follow-up.

CRAFT-IMG: We consider that the participation of 60 women in this sub-study will provide useful information for planning future research; this is achievable by recruiting at 2 sites (UCLH and St Thomas' Hospital): 30 women with cervix $>25\text{mm}$ and 30 women with cervix $\leq 25\text{mm}$ (15 women with cerclage, 15 women without).

If we have data from participants in this study of their cervical length and/or quantitative fetal fibronectin we will be able to carry out predictive statistics. This would involve calculating ROC curves for prediction of spontaneous preterm birth for both fibronectin and transvaginal cervical

length measurement as a continuous variable, for delivery <24, <30, <34 and <37 weeks gestation. From the optimal thresholds, predictive statistics will be calculated.

6. Participant inclusion and exclusion criteria

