Primary objective	
 1. CRAFT-OBS: To assess the risk of preterm birth or late miscarriage in women following an in labour caesarean section 2. CRAFT-RCT: To assess if cervical cerclage reduces preterm birth in pregnant women with a short cervix following a previous in labour caesarean section 3. CRAFT-IMG: To assess if alterations in MRI parameters or ultrasound characteristics occurs in women who undergo a late miscarriage or preterm birth following an in labour caesarean section.
Trial Design	Prospective observational study, nested randomised controlled trial and imaging sub-study in a selected cohort
Endpoints	Incidence of preterm birth at < 34 weeks gestation
Sample Size	CRAFT-OBS: 2200 women, CRAFT-RCT: 1000 women, CRAFT-IMP: 60 women

Study Protocol: **Cerclage After Full-dilatation caesarean-section**

IRAS ID:261294

REC: REC 19/LO/1270

Version 2.0

Date: 10.09.19

Summary of eligibility criteria	CRAFT-OBS: pregnant women 14 ⁺⁰ -23 ⁺⁶ week with a previous history of caesarean section in labour. CRAFT-RCT: pregnant women with a previous history of caesarean section carried out at full dilatation and a short cervix ($\leq 25\text{mm}$) in current pregnancy. CRAFT-IMG: pregnant women with a previous history of caesarean section carried out at full dilatation (30 women with cervix $>25\text{mm}$; 30 CRAFT-RCT participants).
Maximum duration of treatment of participant	Until delivery or removal of cerclage at 37 weeks gestation
Version and date of final protocol	Version 2.0 (10/09/19)
Version and date of protocol amendments	To be inserted

[figure not shown]

Figure 1: Flow of participants through CRAFT project

STUDY SYNOPSIS.....	4
LAY SUMMARY.....	8
PROFESSIONAL SUMMARY	8
GLOSSARY OF TERMS	11
1. Introduction.....	12
1.1. Background.....	12
1.2. Rationale for study.....	13
Study aims and objectives	15
2.	
2.1. Aims.....	15
2.2. Study objectives	15
2.2.1. CRAFT-OBS: a study of risk and management in women with a history of CS in labour	15
2.2.2. CRAFT-RCT: a trial of USS indicated cerclage in women with history of FDCS	16
2.2.3. CRAFT-IMG: a sub-study evaluating imaging methods for assessing risk and management of women with a history of FDCS.....	16
3. Study Design	16
3.1. CRAFT-OBS.....	16
3.2. CRAFT-RCT	16
3.3. CRAFT-IMG	17
3.4. Expected study duration	17
4. Study Endpoints	17
4.1. CRAFT-OBS.....	17
4.2. CRAFT-RCT	18
4.3. CRAFT-IMG	18
5. Sample size and power calculation	19

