We will screen all pregnant women with a history of caesarean section in labour booked for maternity care at all participating sites with transvaginal ultrasound and quantitative fetal fibronectin (if available) between 14⁺⁰ and 23⁺⁶ weeks with a previous in labour CS. These women will be grouped into:

1. Unknown dilatation at time of CS in labour.
2. Dilated 4cm to 9cm at time of CS in labour.
3. Full dilatation at time of CS in labour.

This part of the project will allow us to:

1. Determine pregnancy outcomes in women who have had previous in-labour CS.
2. Evaluate risk of PTB/LM according to degree of dilatation in previous in-labour CS.

Study Protocol: **Cerclage After Full-dilatation caesarean-section**

IRAS ID:261294

REC: REC 19/LO/1270

Version 2.0

Date: 10.09.19

3. Evaluate the predictive value of quantitative fetal fibronectin in women with previous CS in labour if done by direct care team for clinically indicated reasons at any point
4. Evaluate the predictive value of transvaginal ultrasound and whether cervical defects can be identified if performed by direct care team for clinically indicated reasons at any point.
5. Identify women who require referral into specialist preterm surveillance clinics.
6. Identify potential participants for CRAFT-RCT (see Figure 1).

CRAFT-RCT: a trial of USS indicated cerclage in women with history of FDCS

The aim of this trial is to evaluate efficacy of cervical cerclage in pregnant women with a short cervix ($\leq 25\text{mm}$) on TVS between 14⁺⁰ and 23⁺⁶ weeks gestation following a FDCS. The study will allow us to evaluate the impact of cervical cerclage on:

1. Primary obstetric outcome – spontaneous preterm birth rate < 34 weeks gestation.
2. Secondary outcomes - Short-term pregnancy and neonatal outcomes, including a composite of neonatal death and morbidity.

CRAFT-IMG: a study evaluating imaging methods for assessing risk and management of women with a history of FDCS

This imaging sub-study will focus on analysis of TVS and magnetic resonance imaging (MRI) of cervical defects in this population to elucidate which women are at increased risk of PTB/LM. Assessment of any identified cervical defect and its relation to a cervical cerclage will also help us to establish which women at risk of PTB would benefit from this treatment.

Objectives of the imaging study:

1. To assess whether cervical abnormalities can be visualised in the cervix by TVS and MRI.

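### CRAFT-RCT's 1000 women and 80% power do not fit inside the 2200-woman CRAFT-OBS cohort through which they are described as being recruited

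*Combined protocol and SAP*

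**What the plan says.** The synopsis describes the design as "Prospective observational study, nested randomised controlled trial and imaging sub-study in a selected cohort" and gives the sizes as "CRAFT-OBS: 2200 women, CRAFT-RCT: 1000 women". The routes into the trial all start from the observational study:

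- Sections 1.2 and 3.1 invite CRAFT-OBS participants who have had an FDCS and have a short cervix.
- Section 7.1 opens its CRAFT-RCT paragraph by making CRAFT-OBS participants eligible, and excludes women whose records cannot be reviewed to confirm the FDCS.
- Section 7.3 keeps women who decline randomisation in the observational arm.

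Section 3.1 fixes CRAFT-OBS at 2200 women with any previous caesarean in labour. Section 5 derives that number from the precision wanted for a preterm birth rate and links it to sites: "We aim to recruit 324 of these (50%) at a minimum of 7 study sites", then, because at St Thomas' "rather fewer deliveries (11%) are caesareans in labour; so we will aim for at least 20 sites".

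For CRAFT-RCT, section 5 states "Pilot data indicates that at least 10% of all births and 70% of preterm births associated with FDCS occur before 34 weeks", then "In order to detect a reduction in this rate from 10% to 5% 474 women are required in each group to give 80% power", and "We will aim to recruit 500 in each arm in order to allow for 5% loss to follow-up". It gives no FDCS share, short-cervix share, consent rate or number to be screened. Section 3.2 places the trial in at least 41 hospitals over 27 months and says that all women with an FDCS history will have cervical length monitoring.

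**The concern.** Two planned sizes in the same document appear to conflict. The trial needs 1000 women who have both a previous FDCS and a cervix of 25 mm or less. The cohort they are said to come from is 2200 women with any in-labour caesarean, and section 1.1 puts at most a fifth of such caesareans at full dilatation. On that reading the FDCS women in the cohort number fewer than half of those to be randomised, even before the short-cervix criterion.

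What is at stake is the 80% power for the trial's primary endpoint, delivery before 34 weeks. A funder, steering committee or DMC cannot tell from the text whether 1000 is reachable. Section 5 shows how sites add up to the target for CRAFT-OBS but gives nothing comparable for the trial.

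**Working it through.** **1. The plan's own figure.** Inputs from section 5: p1 = 0.10, p2 = 0.05, power 80%; 1:1 allocation from section 3.2. Significance level and sidedness are not stated; I assume two-sided 5%.

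Uncorrected size per arm: n = [1.96·√(2 × 0.075 × 0.925) + 0.842·√(0.10 × 0.90 + 0.05 × 0.95)]² / 0.05² = (0.730 + 0.312)² / 0.0025 = 434.4.

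With continuity correction: n/4 × [1 + √(1 + 4/(n × 0.05))]² = 473.6, so 474. Then 474/0.95 = 499, consistent with 500 per arm. The formula and inflation are correct.

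**2. FDCS women expected in 2200.**

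- Section 1.1: up to 20% of in-labour caesareans are at full dilatation. 2200 × 0.20 = 440.
- Professional summary with section 5: over 25% of deliveries are caesareans and at least one in seven of those is at full dilatation, so about 0.25/7 = 3.57% of deliveries. Section 5 takes 16.2% of deliveries as emergency caesareans. Treating those as the in-labour ones, 3.57/16.2 = 22.0%, and 2200 × 0.2205 = 485.

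Both assume that the cohort's mix follows these shares, with no enrichment for FDCS.

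**3. Against the target.** 1000/440 = 2.3 and 1000/485 = 2.1, so the target is more than twice the expected FDCS women. 1000/2200 = 45% of the whole cohort would have to be FDCS, short-cervix, documented and consenting. If every FDCS woman were randomised, CRAFT-OBS would still need 1000/0.2205 ≈ 4,540 to 1000/0.20 = 5,000 women.

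**4. Power if every FDCS woman in the 2200 were randomised (10% vs 5%).** Power = Φ{[0.05 − c − 1.96·√(2 × 0.075 × 0.925/n)] / √(0.1375/n)}, with c = 1/n (corrected) or 0 (uncorrected) and n per arm.

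| Women | Per arm | Corrected | Uncorrected | Expected events |
|---|---|---|---|---|
| 440 | 220 | 44% | 51% | 33 |
| 485 | 242.5 | 48% | 55% | 36 |
| 948 (plan, after loss) | 474 | 80% | 83% | 71 |

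After the plan's 5% loss, 440 becomes 418 (42% to 49%) and 485 becomes 461 (46% to 53%). The short-cervix, records and consent requirements would lower these further.

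**5. The wider reading.** Suppose all 41 hospitals contribute. Following section 5, I take 4,000 deliveries a year per hospital and use the in-labour caesarean count as the count of women presenting with a previous one. I assume that 11% to 16.2% holds across sites, with a 20% FDCS share, over 24 months (section 3.4) to 27 months (section 3.2).

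- Low: 41 × 4,000 × 0.11 × 2 × 0.20 = 7,216.
- High: 41 × 4,000 × 0.162 × 2.25 × 0.20 = 11,956.

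Then 1000 is 14% to 8% of FDCS women. If the 50% recruitment rate set for CRAFT-OBS is carried over, the supply halves to about 3,610 to 5,980 and 1000 is 28% to 17%. Whether either range is achievable depends on the short-cervix share, which the plan does not give.

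**The case against.** The best defence is that the trial was never meant to be confined to the 2200. Section 3.2 names at least 41 hospitals against at least 20 for CRAFT-OBS, and says all FDCS women will be monitored and randomised if the cervix shortens. Section 7.1 has the direct care team refer FDCS women for surveillance. The eligibility criteria in sections 6.1 and 6.2 do not require CRAFT-OBS enrolment, and section 7.1 makes CRAFT-OBS participants eligible without saying that only they are. The 2200 is a precision requirement, not a ceiling. The figure showing participant flow is not available here and may settle the matter.

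All of this stands, and it limits the conclusion. It does not remove the conflict: each description of how a woman reaches randomisation passes through CRAFT-OBS, and no available sentence opens another route or says that CRAFT-OBS will exceed 2200.

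Several stronger readings are tempting and are not supported:

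- **That 440 is a hard maximum.** The documents' other figures give about 485, and no quota prevents enrichment for FDCS.
- **That 41 hospitals would also fall short.** Step 5 shows that this turns on carrying over a CRAFT-OBS recruitment rate and on a short-cervix share found nowhere in the plan.
- **That 474 or 500 is miscalculated.** Both reproduce.
- **That 10% is the wrong control rate.** It is given as at least 10% of all births after FDCS, while the trial takes only women with a short cervix, a group the professional summary calls high risk. But section 1.1 says it is unknown whether a short cervix predicts outcome after FDCS, so 10% could hold, and a higher rate would raise power for a halving. The assumption needs stating; the documents do not show it to be false.

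**Conclusion.** Wrong as written on the nested reading: a cohort of 2200 does not deliver 1000 randomised FDCS women or 80% power. At the documents' own shares it holds about 440 to 485 FDCS women, and randomising all of them gives about 44% to 55% power for 10% versus 5%. This rests on a two-sided 5% test, on a cohort mix that follows the quoted FDCS shares, and on entry being limited to the 2200.

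A reader might infer that the trial cannot recruit its target. The documents do not support that, because wider recruitment may be intended and the flow figure is not shown. What can be said is that the available text neither states a source for the 1000 beyond CRAFT-OBS nor gives the yield needed to judge it. This should be fixed; confidence is moderate.

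**What to change.** Rewrite the CRAFT-RCT paragraph of section 5 and align the synopsis and sections 1.2, 3.1, 3.2, 7.1 and 7.3.

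1. State that women may be randomised from outside the 2200, or that CRAFT-OBS will exceed 2200. If neither is intended, restate the trial size and the power that 2200 can deliver.
2. If 1000 is kept, support it with a projection: the FDCS share and the number of FDCS women to be screened, equal to 1000 / (short-cervix share × records available × consent). For illustration only, an assumed short-cervix share of 40% to 10% with full records and consent means 2,500 to 10,000 FDCS women.
3. Say that the 10% control rate describes all births after FDCS and is being assumed for women with a cervix of 25 mm or less.
4. State the significance level and sidedness behind 474.

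The cost is one paragraph, a short projection and matching wording elsewhere, with no added visits. If the answer to item 1 changes the trial target or the size of CRAFT-OBS, that is a substantive amendment.
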